#### **4.6.4 QT interval prolongation**

Anlotinib can prolong the QT/QTc interval, which may increase the risk of ventricular tachyarrhythmias (e.g., torsades de pointes) or sudden death. Therefore, patients with congestive heart failure, electrolyte abnormality, or receiving medications known to prolong the QTc interval should undergo regular (every 3–6 weeks) electrocardiogram and electrolyte (sodium, magnesium, potassium, and calcium) tests. If the results of two consecutive independent ECG show QTc interval  $> 500$  ms, anlotinib should be interrupted until QTc interval is  $\leq 480$  ms or returns to baseline level (if QTc interval at baseline is  $> 480$  ms), then the administration can be continued at a lower dose with close ECG monitoring.

For patients with any grade of QTc prolongation ( $\geq 450$  ms) accompanied by torsades de pointes, polymorphic ventricular tachycardia, symptoms or signs of severe arrhythmia, permanent discontinuation of the study drug and specialized cardiovascular treatment are recommended.

Patients with underlying cardiac dysfunction should undergo echocardiography every 6 weeks, and discontinuation is recommended for patients with a left ventricular ejection fraction  $< 50\%$ .

#### **4.6.5 Proteinuria and renal function abnormal**

Proteinuria is one of the common adverse reactions of VEGFR inhibitors. Therefore, urinalysis should be performed weekly for patients throughout the treatment. Patients with urine protein  $\geq ++$  for 2 consecutive tests should undergo a 24-hour urine protein test. Measures including treatment interruption, dose adjustment and permanent discontinuation are recommended according to the severity of adverse reactions (Table 1).

Recommended drugs: Compound Nephritis Tablets. ACEIs and ARBs can be provided as they can lower renal tubular pressure and thereby alleviate proteinuria and reduce the risk of potential adverse cardiac events.

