### 4.3 Route of Administration

Based on the human pharmacokinetic studies, 12 mg qd for 2 consecutive weeks followed by 1-week discontinuation was generally recognized as the recommended regimen for subsequent studies, and 12 mg qd was the maximum tolerated dose. In addition, the study results showed that the  $t_{max}$  of anlotinib in humans was increased with a high-fat diet as compared to administration under fasting conditions, and drug absorption was slightly reduced (approximately 80% that of administration under fasting conditions). Therefore, anlotinib is recommended to be administered under fasting conditions in subsequent clinical practice.

Anlotinib hydrochloride will be administered orally to all enrolled patients at a dose of 12 mg qd before breakfast, for 2 consecutive weeks, and discontinued for 1 week, i.e., three weeks (21 days) as a course of treatment. Treatment should continue until disease progression or occurrence of intolerable adverse reactions.

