### 4.4 Dose Adjustment

Adverse reactions should be closely monitored during the administration of the study drug, and the dose should be adjusted according to the patient's tolerance. Adverse reactions caused by the study drug can be treated by symptomatic treatment, drug interruption and/or dose adjustment. The dose should be adjusted under the guidance of a physician according to the severity of adverse reactions: 1) First dose adjustment: 10 mg qd for 2 weeks, followed by 1-week discontinuation; 2) Second dose adjustment: 8 mg qd for 2 weeks, followed by 1-week discontinuation. If the dose of 8 mg remains intolerable, the drug should be permanently discontinued.

Dose adjustments for each adverse reaction are as follows:

- **Hematologic Toxicities**

(1) Platelet count decreased

Grade of AE	Treatment Recommendations	Dose Adjustment
Grade 1	Perform visits as scheduled	Maintain the original dose

Grade 2	Delay dosing until AE resolves to $\leq$ grade 1	Maintain the original dose
Grade 3	Delay dosing and provide medical interventions until AE resolves to $\leq$ grade 1	Continue at a lower dose
Grade 4	Permanent discontinuation	/

(2) Neutrophil count decreased

Grade of AE	Treatment Recommendations	Dose Adjustment
Grade 1	Perform visits as scheduled	Maintain the original dose
Grade 2	Delay dosing until AE resolves to $\leq$ grade 1	Maintain the original dose
Grade 3-4	Delay dosing and provide medical interventions until AE resolves to $\leq$ grade 1	Continue at a lower dose

● **Non-Hematologic Toxicities**

(1) Hepatic function abnormal (elevated ALT, AST or TBIL)

Grade of AE	Treatment Recommendations	Dose Adjustment
Grade 1	Perform visits as scheduled	Maintain the original dose
Grade 2	Delay dosing until AE resolves to $\leq$ grade 1	Maintain the original dose
Grade 3-4	Delay dosing and provide medical interventions until AE resolves to $\leq$ grade 1	Continue at a lower dose

(2) Proteinuria

Grade of AE	Definition	Treatment Recommendations	Dose Adjustment
Grade 1	1+ proteinuria, or urine protein $<$ 1.0 g/24 h	Perform visits as scheduled	Maintain the original dose
Grade 2	2+ proteinuria, and urine protein $<$ 1.0 g/24 h	Perform visits as scheduled	Maintain the original dose
	2+ proteinuria, and urine protein is 1.0–3.4 g/24 h	Delay dosing and provide medical interventions until proteinuria $\leq$ 2+ and urine protein $<$ 1.0 g/24 h	Maintain the original dose

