### **5. STUDY PROCEDURES**

Patients must read and sign the informed consent form (ICF) approved by the Ethics Committee (EC) prior to the study. The examinations for subjects and test procedures should be conducted according to the schedule of the clinical study, irrespective of the duration of drug discontinuation. Changes due to holidays, festivals and other administrative reasons are allowed within the time window of each examination.

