## **5.3 Treatment Period**

- The following assessments should be completed before each dose in each cycle. If the test is completed within 7 days before the first dose during the screening

period, it is not required prior to the first dose.

- ✓ ECOG score;
- ✓ Vital signs: Pulse, respiratory rate, body temperature, blood pressure;
- ✓ Physical examination: General conditions, head and face, skin, lymph nodes, neck, eyes, ENT, oral cavity, respiratory system, cardiovascular system, abdomen, reproductive-urinary system, musculoskeletal system, nervous system, mental status, and others;
- ✓ Blood routine: Complete blood count and differential count (white blood cells, red blood cells, lymphocytes, monocytes, neutrophils, basophils, eosinophils, hemoglobin), platelet count;
- ✓ Clinical chemistry: ALT, AST, GGT, total bilirubin, direct bilirubin, AKP, blood urea nitrogen or urea (blood urea nitrogen is preferred), total protein, albumin, creatinine, blood glucose, lactate dehydrogenase, K+, Na+, Ca2+, Mg2+, Cl;
- ✓ EBV-DNA test;
- ✓ Urinalysis: White blood cell count, red blood cell count, urine protein. If urine protein is  $\geq 2+$ , a 24-hour urine protein test is required;
- ✓ Routine stool test: White blood cells, red blood cells, occult blood;
- ✓ Coagulation function: Prothrombin time, activated partial thromboplastin time, thrombin time, fibrinogen, D-dimer, international normalized ratio;
- ✓ Thyroid function: TSH, FT3, FT4 (FT3 and FT4 can be replaced by T3 and T4 if they are not available);
- ✓ 12-lead electrocardiogram (12-Lead ECG): Additional necessary tests should be performed according to the judgment of the investigators in case of any abnormality;
- ✓ Concomitant medication: Concomitant medication should be recorded in detail;
- ✓ AEs: AEs should be recorded in detail;
- Radiological examination (completed before dosing every two cycles): CT or MRI of the nasopharynx, neck, chest, and abdomen (including the pelvis). An enhanced scan is preferred if not contraindicated. The radiological examination should be performed every 6 weeks. For bone metastases, a bone scan is

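### During treatment, section 4.6.5 triggers the 24-hour urine protein test after two consecutive results of 2+ or more and section 5.3 after one, and the weekly urinalysis of 4.6.5 is absent from the section 5 schedule

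*Protocol*

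**What the plan says.** Three parts of the protocol bear on urine protein during treatment.

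- **Section 4.6.5** (management of proteinuria) states that "urinalysis should be performed weekly for patients throughout the treatment". Patients at ++ or above "for 2 consecutive tests should undergo a 24-hour urine protein test". For the resulting dosing measures it sends the reader to a Table 1.
- **Section 5.3** (treatment-period schedule) opens its list with "The following assessments should be completed before each dose in each cycle". Urinalysis is on that list. If the result is 2+ or more, "a 24-hour urine protein test is required", with no repeat test first. Sections 5.1 (screening) and 5.5 (early termination) use the same single-result rule.
- **Section 4.4** (dose adjustment) has a proteinuria table in which the 24-hour amount decides the row. One of the two rows for a 2+ result is defined as "2+ proteinuria, and urine protein is 1.0–3.4 g/24 h".

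Section 4.3 fixes the cycle: dosing "for 2 consecutive weeks, and discontinued for 1 week, i.e., three weeks (21 days) as a course of treatment". The introduction to section 5 adds: "The examinations for subjects and test procedures should be conducted according to the schedule of the clinical study".

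**The concern.** The same event, a first dipstick result of 2+ during treatment, makes the 24-hour test mandatory in one section and does not yet trigger it in another. The 24-hour amount is an input to the dosing table, so the trigger determines when a patient can be placed in a row of that table.

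The frequency instruction raises a second, smaller problem. It stands in the toxicity-management text and not in the visit schedule that sites are told to follow.

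Two things are at stake. One is patient safety: when a clinically relevant protein loss is quantified and acted on. The other is consistent ascertainment. Section 2.1 places safety in the primary objective, section 9.3.2 will calculate adverse event incidence, and section 11.1.2 speaks of several participating hospitals. If hospitals follow different sections, the recorded frequency and grade of proteinuria will partly reflect which section each one used.

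**Working it through.** The protocol gives no figure to reproduce here. The check is a side-by-side reading with simple counts.

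**Step 1: trigger for the 24-hour test**

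| Section | When it applies | Trigger |
|---|---|---|
| 5.1 | Screening | One result of 2+ or more |
| 5.3 | Treatment | One result of 2+ or more |
| 5.5 | Early termination | One result of 2+ or more |
| 4.6.5 | Treatment | 2+ or more on two consecutive tests |

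Sections 5.3 and 4.6.5 cover the same period and differ. The two-test wording appears only in 4.6.5. That shows which text is the outlier, not which rule is right.

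**Step 2: what the 24-hour amount decides (section 4.4)**

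| Finding | Dosing consequence in 4.4 |
|---|---|
| 2+ and below 1.0 g/24 h | Visits as scheduled, original dose |
| 2+ and 1.0–3.4 g/24 h | Dosing delayed, then original dose |
| 3.5 g/24 h or more | Dosing delayed, then lower dose |

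Without a 24-hour amount, a patient with a 2+ dipstick cannot be placed in either 2+ row, and the third row is defined by the 24-hour amount alone.

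**Step 3: time from first positive result to trigger**

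- Under 5.3: 0 days, because one result suffices.
- Under 4.6.5 as written: one test interval, about 7 days with weekly testing, and only if the second test is also positive. If it is negative, the test is not triggered.

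**Step 4: tests per 21-day cycle**

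- 4.6.5, weekly: 21 / 7 = 3.
- 5.3, read as once per cycle: 1. This is the natural reading, because the same list holds physical examination, ECG, thyroid function and coagulation, and because tests done within 7 days before the first dose need not be repeated.
- 5.3, read literally as before every dose: 14, one for each once-daily dose over two weeks.

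Neither reading of 5.3 yields weekly testing.

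**Step 5: is one section uniformly earlier?** Assume that urine protein rises to 2+ on some day and stays there, and that tests are evenly spaced.

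- 4.6.5: the first positive comes 0 to 7 days after the rise and the second 7 days later, so the trigger falls at 7 to 14 days.
- 5.3, once per cycle: the first positive is the trigger, at 0 to 21 days.

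The ranges overlap. Weekly testing can find the first positive sooner, while the two-test rule acts on it later. The direction of the difference therefore depends on when the rise occurs within the cycle.

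**The case against.** The strongest reply is that a site can comply with both sections.

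- **Frequency.** Section 5.3 sets a visit panel and does not forbid tests between visits. Section 4.6 adds toxicity-specific monitoring elsewhere too: 4.6.3 asks for blood pressure daily for 6 weeks and then 2–3 times a week, although blood pressure is also in the 5.3 panel. A reader might infer that the two sections flatly contradict each other on frequency. The text does not support that: 5.3 never says once per cycle, and weekly tests can be read as additional. What stands is that section 5, the working schedule, does not contain the weekly test.
- **Trigger.** Section 4.6.5 does not say that the 24-hour test may be done only after two positives, so ordering it after every single positive would breach neither section. A reader might infer that sites are given rules that cannot both be followed, and that is too strong. Even so, a site that relies on 4.6.5 would wait for a second result, while 5.3 makes the test mandatory at the first.
- **Precedence.** The introduction to section 5 directs sites to the study schedule, which favours 5.3. It is not a clause saying which section governs when management text and schedule differ.
- **Impact.** A patient at 2+ with less than 1.0 g/24 h stays on the original dose under either trigger, so timing changes dosing only at higher amounts. Safety analysis is descriptive and there is one arm, so no comparison between treatments is distorted. Both points stand and limit the size of the concern.

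**Conclusion.** The point holds as an inconsistency in site instructions that should be corrected. The trigger conflict is direct. After a first 2+ result, the 24-hour test is due at once under 5.3. Under 4.6.5 it is due about 7 days later, assuming weekly testing, and only if the second result is also positive. The consequence for dosing is confined to patients whose 24-hour amount would be 1.0 g or more. The missing weekly test in section 5 is an omission, with a size of 1 test against 3 per cycle if 5.3 is read as once per cycle.

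Two larger figures are tempting but not supported. A delay of about three weeks arises only if a site takes its frequency from 5.3 and its trigger from 4.6.5, a combination that neither section prescribes. A total over several cycles, such as 18 tests against 6 over 6 cycles, needs a treatment duration that this protocol does not set, since treatment runs to progression or intolerable toxicity.

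Nothing here touches the sample size or the DCR decision rule, and no view is taken on which frequency or trigger is clinically right.

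**What to change.** 1. Reconcile 4.6.5 and 5.3 so that one urinalysis schedule and one trigger for the 24-hour test apply during treatment. The clinical lead chooses both.
2. Carry the chosen schedule into section 5, so that a site working from it alone performs every intended test, and replace the wording about each dose in each cycle with an unambiguous timing.
3. In 4.6.5, replace the reference to Table 1 with a reference to the proteinuria table in 4.4. In the text at hand, the tables labelled Table 1 are the list of anti-angiogenic drugs in section 1.3 and a response table in Appendix II. The 4.4 table carries no number.
4. Check that the chosen trigger always provides the 24-hour amount where the 4.4 table needs it.

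The cost is a wording amendment and, depending on the choice, a change in the number of dipstick tests and 24-hour collections. The statistical design does not change.

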#### **4.6.6 Thyroid insufficiency**

In the ALTER0303 study, hypothyroidism was observed in 58 patients (19.39%) of the anlotinib group, including 1 patient (0.34%) with grade 3 hypothyroidism. Grade 1 hypothyroidism was observed in 4 patients (2.80%) of the placebo group. Thyroid function should be tested prior to the first dose and closely monitored throughout the treatment for all subjects. All subjects receiving anlotinib should be closely monitored for symptoms and signs of decreased thyroid function, including cold intolerance, decreased appetite, and edema. Patients with underlying hypothyroidism or hyperthyroidism should be given appropriate standard treatment when receiving anlotinib. Thyroid function [thyroid stimulating hormone (TSH), triiodothyronine (T3), tetraiodothyronine (T4)] should be tested every 3–6 weeks for patients with symptoms and signs of thyroid insufficiency. When TSH  $\geq$  20 mU/L or T3, T4, FT3 or FT4 is lower than the normal value, symptomatic treatment (e.g., Euthyrox) should be given as soon as possible.

#### **4.6.7 Hand and foot skin reaction**

Hand and foot skin reaction is characterized by redness, obvious discomfort, swelling, and tingling sensation in the palms or soles. It is one of the common clinical adverse reactions of VEGFR inhibitors.

Clinical manifestations of hand and foot skin reaction: Grade 1: Minor painless skin changes or dermatitis (e.g., erythema, edema, or hyperkeratosis); Grade 2: Painful skin changes (e.g., peeling, blistering, bleeding, swelling, or hyperkeratosis) affecting instrumental activities of daily living; Grade 3: Painful severe skin changes (peeling, blistering, bleeding, edema, or hyperkeratosis) affecting personal activities of daily living.

Patients with grade 1 hand and foot skin reaction should continue to be observed. Patients with grade 2 hand and foot skin reaction should be treated symptomatically, including strengthening skin care, keeping the skin clean, avoiding secondary

infections, compression and friction, topical use of lotions or lubricants containing urea and corticosteroids, and topical use of antifungal agents or antibiotics in case of infections under the guidance of a dermatologist.

Patients with grade  $\geq 3$  hand and foot skin reaction should continue treatment at a lower dose. Discontinuation is recommended if the adverse reaction persists.

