#### (5) Hand and foot skin reaction

Grade of AE	Treatment Recommendations	Dose Adjustment
Grade 1-2	Perform visits as scheduled	Maintain the original dose
Grade 3-4	Delay dosing until AE resolves to $\leq$ grade 2	Continue at a lower dose

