## **4.6 Adverse Reactions and Treatment**

### **4.6.1 Hemorrhage**

VEGFR inhibitors can increase the risk of hemorrhage. Clinical studies showed that anlotinib increased the incidence of hemorrhage events compared with placebo. Therefore, clinicians should pay close attention to relevant symptoms and closely monitor the prothrombin time and international normalized ratio (INR) during dosing.

Once a grade 2 hemorrhage event is observed, treatment should be interrupted; if the severity of the event improves to < grade 2 within 2 weeks, treatment should be continued at a lower dose. Permanent discontinuation is required in case of hemorrhage events of grade 3 or higher.

Active symptomatic treatments should be provided for digestive tract hemorrhage, including fecal occult blood  $\geq ++$ , hematemesis or bloody stool. Patients with upper gastrointestinal hemorrhage should be fasted and given acid suppression agents, medications for gastric mucosa protection, hemostasis (e.g., tranexamic acid, reptilase), blood transfusion and supportive treatments. Patients with lower gastrointestinal hemorrhage should be given hemostasis, blood transfusion and supportive treatments. Patients with unmanageable hemorrhage should be treated with surgical assistance.

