#### **4.6.3 Increased blood pressure**

Increased blood pressure is the most common adverse reaction of VEGFR inhibitors. Previous clinical studies have shown that the incidence of hypertension events was high (about 13.61% for grade 3 or higher) in patients receiving Anlotinib Hydrochloride Capsules. Therefore, blood pressure should be measured daily for the first 6 weeks of dosing and 2–3 times a week during the subsequent dosing period.

In case of hypertension, the investigators are recommended to handle the event as follows:

- Grade 1: Prehypertension (SBP 120–139 mmHg or DBP 80–89 mmHg):  
Lack of indications for antihypertensive drugs, only blood pressure

monitoring is required;

- Grade 2: Stage I hypertension (SBP 140–159 mmHg or DBP 90–99 mmHg): Requires medical interventions; Repeated or persistent ( $\geq 24$  h), symptomatic SBP increases by  $> 20$  mmHg or increases to  $> 140/90$  mmHg compared to previous normal range; Requires monotherapy and blood pressure monitoring; Thiazide diuretics are commonly used, and angiotensin-converting enzyme inhibitors (ACEIs), angiotensin II receptor blockers (ARBs),  $\beta$ -blockers, and calcium channel blockers may also be considered;
- Grade 3: Stage II hypertension (SBP  $\geq 160$  mmHg or DBP  $\geq 100$  mmHg): Requires medical intervention; Requires multi-drug therapy, usually thiazide diuretics combined with ACEIs,  $\beta$ -blockers or calcium channel blockers;
- Grade 4: Life-threatening (e.g., malignant hypertension, transient or permanent neurologic deficit, hypertension emergency): Requires urgent intervention;

If grade 3/4 hypertension (SBP  $\geq 180$  mmHg or DBP  $\geq 110$  mmHg) is observed, anlotinib should be interrupted; If grade 3/4 hypertension is observed after anlotinib resumption, treatment should be continued at a lower dose. If grade 3/4 hypertension persists, discontinuation is recommended.

- Hypertension emergencies are defined as having DBP  $> 120$  mmHg accompanied by acute or progressive target organ damage (such as brain infarction, intracranial or subarachnoid hemorrhage, and hypertensive encephalopathy). Progressive or accelerated hypertension on the basis of chronic primary hypertension is the most common (about 40% to 50%) hypertension emergency. Treatment should be discontinued once a hypertension emergency is observed. The subject should withdraw from the clinical study and receive specialized cardiovascular treatment in time.

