#### **4.6.8 Gastrointestinal adverse events**

In the ALTER0303 clinical study, diarrhea was the most frequently reported treatment-related gastrointestinal AE. Diarrhea was reported by 86 patients (29.25%) in the anlotinib group, including 3 patients (1.02%) with grade 3 diarrhea. Other gastrointestinal AEs included oropharyngeal pain, stomatitis, vomiting, nausea, and abdominal pain. Supportive care for gastrointestinal AEs requiring treatment may include oral care, antiemetic and antidiarrheal treatments.

Supportive treatments may be given for patients experiencing grade 1–2 diarrhea throughout study, such as symptomatic treatment (e.g., 4 mg oral loperamide, then 2 mg every 2 hours until diarrhea resolves) at the time of onset. If grade 3/4 diarrhea is observed, anlotinib should be interrupted. If grade 3/4 diarrhea is observed again after anlotinib resumption, treatment should be continued at a lower dose. If the adverse reaction persists, discontinuation is recommended.

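### For Grade 3 or higher hand-foot skin reaction, the table in 4.4 holds anlotinib until Grade 2 or lower before reducing the dose, while 4.6.7 reduces the dose and states no hold

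*Protocol*

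**What the plan says.** Two parts of the protocol cover the same event at the same severity.

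- **Section 4.4, table (5), Grade 3-4.** The treatment recommendation is "Delay dosing until AE resolves to" Grade 2 or lower. The dose-adjustment column then continues treatment at a lower dose.
- **Section 4.6.7, Grade 3 or higher.** Patients with this degree of "hand and foot skin reaction should continue treatment at a lower dose". The next sentence reads "Discontinuation is recommended if the adverse reaction persists".

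The opening text of 4.4 says that adverse reactions "can be treated by symptomatic treatment, drug interruption and/or dose adjustment". It sets the dose steps at 12 mg, then 10 mg, then 8 mg, and presents the tables that follow as the adjustments for each reaction. The protocol does not say which section governs where 4.4 and 4.6 differ.

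**The concern.** A clinician who goes to the 4.6 subsection on this reaction finds an instruction to carry on at a reduced dose. A clinician who goes to the 4.4 table finds an instruction to stop until recovery and only then reduce. The same patient could be managed in two ways, depending on the page consulted.

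The event is not remote. Section 1.5 lists hand-foot skin reaction among the major adverse reactions in the anlotinib phase I study, and 4.6.7 calls it common for VEGFR inhibitors. By the 4.6.7 description, Grade 3 means severe, painful skin changes that interfere with self-care. What is at stake is avoidable exposure during a severe reaction and uneven dosing between sites, not an error in the analysis.

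**Working it through.** The protocol states no figure to reproduce. The check compares the wording and counts the lower-dose instructions.

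**Step 1. The two instructions side by side.**

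| Element | 4.4, table (5), Grade 3-4 | 4.6.7, Grade 3 or higher |
|---|---|---|
| Hold | Yes | Not stated |
| Recovery grade before restart | Grade 2 or lower | Not stated |
| Dose afterwards | Lower | Lower |

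The end point is the same. The difference is whether dosing stops in between.

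**Step 2. What the difference means for a patient.** From 12 mg the first reduction is to 10 mg, and 10/12 = 83% of the starting dose. Under 4.6.7 read alone, a patient with a Grade 3 reaction could stay on 83% of the dose for the rest of the two-week dosing block. Under 4.4 the dose is zero until Grade 2 or lower.

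**Step 3. Lower-dose rows in the 4.4 tables.** These are platelets Grade 3, neutrophils Grade 3-4, hepatic function Grade 3-4, proteinuria Grade 3-4, hemorrhage Grade 2, hypertension Grade 3, hand-foot skin reaction Grade 3-4, and other events Grade 2-3. All 8 of the 8 rows state a delay.

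**Step 4. The 4.6 subsections that prescribe a lower dose.** There are five.

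- *4.6.1, hemorrhage:* the hold is attached to the reduction. "Once a grade 2 hemorrhage event is observed, treatment should be interrupted", and the lower dose follows improvement.
- *4.6.4, QTc:* the hold is attached to the reduction. The drug is interrupted until the interval recovers, "then the administration can be continued at a lower dose with close ECG monitoring".
- *4.6.3, blood pressure:* the hold is stated at the first episode only. Grade 3/4 hypertension "is observed, anlotinib should be interrupted; If grade 3/4 hypertension is observed after anlotinib resumption", the dose is lowered, and no second hold is stated.
- *4.6.8, diarrhea:* the pattern is the same as in 4.6.3. "If grade 3/4 diarrhea is observed, anlotinib should be interrupted" covers the first episode, and the later reduction states no hold.
- *4.6.7, hand-foot skin reaction:* no hold is stated at any step.

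So 2 of the 5 attach a hold to the reduction, 2 of the 5 state one only earlier, and 1 of the 5 states none.

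**Step 5. Does a dose reduction imply a hold by itself?** The opening text of 4.4 joins interruption and dose adjustment with and/or, so it does not. For this event the hold comes from the table row, and 4.6.7 does not repeat it.

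**The case against.** The strongest reply is that 4.6.7 is silent rather than contrary. Section 4.4 has a row for exactly this event and these grades. Section 4.6.7 ends in the same action, forbids no hold, and gives no competing recovery grade or dose level. A site that applies the 4.4 row satisfies both sections, so 4.6.7 may simply abbreviate the step after the hold. This stands in part: the sections are reconcilable, and a reader who infers a flat contradiction goes further than the text allows.

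It does not dispose of the point, because 4.6 cannot be relied on as shorthand for 4.4. For Grade 3 hypertension, table (4) in 4.4 lowers the dose after the first hold, whereas 4.6.3 lowers it only on recurrence. A site therefore has no sound basis for assuming that 4.6.7 silently brings in the hold. Section 7.3.1 does not settle it either: for intolerable symptoms it offers stopping, delaying or symptomatic treatment as alternatives.

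A reader might also infer that 4.6.7 is the only lower-dose instruction in the protocol without a hold. The documents do not support that, since the reduction steps in 4.6.3 and 4.6.8 state none either. What is particular to 4.6.7 is that no hold appears at any step. Nor is it a fair criticism of 4.6.7 alone that it lacks a pointer to 4.4 or sets no time limit on persistence. The four comparison subsections give no pointer to 4.4 either, and 4.6.3 and 4.6.8 also leave persistence without a limit.

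**Conclusion.** The point holds as a minor dosing inconsistency. For Grade 3 or higher hand-foot skin reaction, 4.4 requires a hold until Grade 2 or lower before the dose is lowered; 4.6.7 omits it and, read alone, permits dosing through the reaction. The practical consequence depends on a site following 4.6.7 without the 4.4 table. The protocol gives no rate of Grade 3 hand-foot skin reaction, so the number of patients affected cannot be computed. The DCR decision rule, the error rates and the sample size are unaffected.

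**What to change.** Replace the Grade 3 instruction in 4.6.7 with: *Grade 3 or higher: interrupt anlotinib until Grade 2 or lower, then resume at the next lower dose (see 4.4)*. Keep the present recommendation to discontinue if the reaction persists. This restates the sponsor's own 4.4 rule and changes no other dosing rule. The cost is one sentence and a notice to sites, with no new data, visits or patients.
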